5.3. Lifestyle Considerations

No restrictions are required.

5.4. Screen Failures

Screen failures are defined as participants who consent to participate in the clinical study but are not subsequently assigned to study treatment in the study.

Tests with results that fail eligibility requirements may be repeated once during screening if the investigator believes the result to be in error. Additionally, a participant who fails screening may repeat the screening process 1 time if the investigator believes that there has been a change in eligibility status. For screening assessments that are repeated, the most recent available result before treatment assignment will be used to determine eligibility. Participants who rescreen must re consent and be assigned a new participant number.

5.5. Replacement of Participants

No participants will be replaced at any time during this study.

5.6. Data Monitoring Committee

Preplanned analyses of safety will be provided to an independent DMC as specified in the DMC charter. The DMC will review safety data of the ongoing study approximately 8 weeks after the first 10 participants have been treated. In addition, the DMC will make recommendations to the

sponsor at the planned interim futility analysis. The DMC will use the guidelines provided in Section 10.5 for recommendation of either continuation or early termination of the study at the interim analysis. The process by which the DMC will make recommendations and decisions will be documented in the IDMC charter.

6. STUDY TREATMENT

6.1. Study Treatment Administered

Table 6 presents the study treatment information.

Table 6: Description and Administration of Parsaclisib

Compound name	Parsaclisib
Dosage strengths	1 mg, 2.5 mg, 5 mg, and 20 mg
Form	Tablet
Active compound	Parsaclisib
Route of administration	Oral
Dose and regimen	20 mg QD for 8 weeks followed by 2.5 mg QD
Instructions	Parsaclisib will be taken orally with water without regard to food [REDACTED] [REDACTED] Parsaclisib should be taken at approximately the same time each day. If a dose is missed by more than 12 hours, the participant should skip the dose and take the next scheduled dose at the usual time. For QW dose regimen, if the dose is missed by more than 2 days, the participant should skip the dose and take the next scheduled dose.

6.2. Preparation, Handling, and Accountability

6.2.1. Supply, Packaging, and Labeling

Parsaclisib will be provided as 1 mg, 2.5 mg, 5 mg, and 20 mg tablets packaged in high-density polyethylene bottles. No preparation is required.

Each container will be labeled as required per country requirement.

6.2.2. Storage

Bottles of parsaclisib tablets should be stored at ambient conditions (15°C-30°C).

6.2.3. Instruction to Participants for Handling Parsaclisib

The participant must be instructed in the handling of parsaclisib as follows:

- To store study treatment at room temperature.
- To remove from the study treatment bottle only the number of tablets needed at the time of administration.
- Not to remove doses in advance of the next scheduled administration.
- To make every effort to take doses on schedule.
- To report any missed doses.
- To keep parsaclisib in a safe place and out of reach of children.
- To bring all used and unused study treatment kits to the site at each visit.

The investigator, investigational drug storage manager (Japan), or designee is responsible for study treatment accountability, reconciliation, and record maintenance (ie, receipt, reconciliation, and final disposition records). Inventory and accountability records must be maintained and be readily available for inspection by the study monitor and open to inspection at any time by any applicable regulatory authorities. The investigator, investigational drug storage manager, or designee must maintain records that document:

- Delivery of study drug to the study site.
- Inventory of study drug at the site.
- Participant use of the study drug, including tablet counts from each supply dispensed.
- Return of study drug to the investigator, investigational drug storage manager (for Japan) or designee by participants.

The investigational product must be used only in accordance with the Protocol. The investigator will also maintain records adequately documenting that the participants were provided the specified study drug. These records should include dates, quantities, and any available batch or serial numbers or unique code numbers assigned to the investigational product and study participants.

Completed accountability records will be archived by the site. The investigator, investigational drug storage manager, or designee will be expected to collect and retain all used, unused, and partially used containers of study drug until verified by the study monitor (unless otherwise agreed to by the sponsor). At the conclusion of the study, the investigator, investigational drug storage manager, or designee will oversee shipment of any remaining study drug back to the sponsor or its designee for destruction according to institutional SOPs. If local procedures mandate on-site destruction of investigational supply, the site should (where local procedures allow) maintain the investigational supply until the study monitor inspects the accountability records in order to evaluate compliance and accuracy of accountability by the investigative site. At sites where the study drug is destroyed before monitor inspection, the monitors rely on documentation of destruction per the site SOP.

Further guidance and information for the final disposition of unused study treatments are provided in the Pharmacy Manual.

6.3. Measures to Minimize Bias: Randomization and Blinding

Not applicable.

6.4. Study Treatment Compliance

Compliance with all study-related treatments should be emphasized to the participant by the site personnel, and appropriate steps should be taken to optimize compliance during the study. Compliance with parsaclisib will be calculated by the sponsor based on the drug accountability documented by the site staff and monitored by the sponsor/designee (tablet counts). Participants will be instructed to keep a daily diary to record dosing compliance and bring the diary plus all study treatments with them to the study visits for site personnel to conduct tablet counts to assess study treatment accountability. The drug accountability documentation will be used by the sponsor to calculate treatment compliance.

6.5. Dose Modifications

Dose modification guidance for AEs that have been previously observed in participants receiving parsaclisib or are potential class-effect AEs are provided (see Table 7). The starting dose and dose reduction levels of parsaclisib are provided (see Table 8). Individual decisions regarding dose interruption and reduction should be made using clinical judgment and in consultation with the sponsor's medical monitor, taking into account relatedness of the AE to the study treatment and the participant's underlying condition. Adverse events that have a clear alternative explanation or transient (≤ 72 hours) abnormal laboratory values without associated clinically significant signs or symptoms may be exempt from dose-reduction guidelines.

Table 7: Guidelines for Interruption and Restarting of Study Drug

ADVERSE EVENT	ACTION TAKEN
Chemistry	

 • AST and/or ALT is Grade 3 ($> 5.0 \times$ ULN). 
Note: In participants with liver metastasis-related elevations at baseline, contact sponsor to discuss clinical management and possible dose reductions.
	
Step 1: Interrupt parsaclisib and monitor weekly until the toxicity has resolved to \leq Grade 1.
 
Step 2: Restart parsaclisib at next lower dose with medical monitor approval. Monitor as clinically indicated.

Table 7: Guidelines for Interruption and Restarting of Study Drug (Continued)

ADVERSE EVENT	ACTION TAKEN
Hematology	

 • Grade 3 ANC ($< 1.0 \times 10^9/L$). • Platelet count is Grade 2 (50 to $< 75 \times 10^9/L$) for participants who enrolled with platelets $> 100 \times 10^9/L$. • Platelet count is Grade 3 ($< 50 \times 10^9/L$) for participants who enrolled with platelets $\leq 100 \times 10^9/L$. 	
Step 1: Interrupt pascalisib up to 14 days until the toxicity has resolved to \leq Grade 1 or pretherapy baseline. For Grade 3 ANC, monitor at least weekly.
 
Step 2: Restart pascalisib at same dose; monitor as clinically indicated.

 • Grade 4 ANC ($< 0.5 \times 10^9/L$). • Grade 3 or Grade 4 febrile neutropenia. • Platelet count is Grade 4 ($< 25 \times 10^9/L$). 	
Step 1: Interrupt pascalisib up to 14 days until the toxicity has resolved \leq Grade 2. (Monitor ANC at least weekly.)
 
Step 2: Restart pascalisib at same dose. Monitor as clinically indicated. If recurs, start at next lower dose.

Other toxicities	

 • Diarrhea (Grade 1). 	
Step 1: Treat with antimotility agents (eg, 2 mg loperamide followed by 2 mg every 4 hours or after every unformed stool) and initiate supportive care (see Section 6.5.1). Monitor approximately every 48 hours until resolved. If not improved after 48 hours, treat per guidance for Grade 2.

 • Diarrhea (Grade 2). 	
Step 1: Interrupt pascalisib. Perform work-up for infection (including CMV, C. difficile, etc) immediately. Initiate or continue supportive care (see Section 6.5.1). Monitor approximately every 48 hours until resolution.
 
Step 2: If improved within 48 hours and/or infection* is confirmed, restart pascalisib at the same schedule and dose after resolved to \leq Grade 1 and continue to monitor.
 
*For infectious diarrhea/colitis, follow institutional standard-of-care guidelines and restart pascalisib according to clinical judgement after resolved to \leq Grade 1. Consult with medical monitor if needed.
 
Step 3: If not improved within 48 hours and infection is ruled out, start oral steroids, or consider IV steroids if participant is being given IV fluids. If no improvement with oral steroids, switch to IV steroids.
 
Step 4: When diarrhea resolves to \leq Grade 1, continue supportive care and taper steroids according to institutional standard of care. When taper is complete (eg, no steroid or ≤ 10 mg/day prednisone or equivalent) and diarrhea is \leq Grade 1, restart pascalisib at the next lower dose with approval of the medical monitor (see Table 8 for dose levels).
 
Step 5: If Grade 2 diarrhea reoccurs, treat per guidance for diarrhea (\geq Grade 3)/noninfectious colitis.
 
Step 6: If \geq Grade 2 diarrhea reoccurs a third time, permanently discontinue pascalisib.

Table 7: Guidelines for Interruption and Restarting of Study Drug (Continued)

ADVERSE EVENT	ACTION TAKEN						
Other toxicities (continued)							

 • Diarrhea (≥ Grade 3). • Noninfectious colitis (any grade; confirmed or suspected). 	
Step 1: Interrupt piasaalisib. Perform work-up for infection (including CMV, C. difficile, etc) immediately. Initiate or continue supportive care (see Section 6.5.1). Consider colonoscopy with biopsy for diarrhea ≥ Grade 3 and/or if symptoms^a suggestive of colitis. Monitor every 48 hours until resolution.
 
Step 2: If infection* is ruled out, start oral steroids, or consider IV steroids if participant is being given IV fluids. If no improvement with oral steroids within 48 hours, switch to IV steroids.
 
*For infectious diarrhea/colitis, follow institutional standard of care guidelines and restart piasaalisib according to clinical judgement after resolved to ≤ Grade 1. Consult with medical monitor if needed.
 
Step 3: When diarrhea/colitis resolves to ≤ Grade 1, continue supportive care and taper steroids according to institutional standard of care. When taper is complete (eg, no steroid or ≤ 10 mg/day prednisone or equivalent) and diarrhea/colitis is ≤ Grade 1, restart piasaalisib as described herein and with approval of the medical monitor. Continue to monitor.
 
  
 Piasaalisib	Dose Modification	
   
 Any dose with QD dosing	20 mg QW	
 
 20 mg QW	10 mg QW	
  
 
Step 4: If ≥ Grade 3 diarrhea/colitis (any grade) reoccurs, permanently discontinue piasaalisib.
	Piasaalisib	Dose Modification	Any dose with QD dosing	20 mg QW	20 mg QW	10 mg QW
Piasaalisib	Dose Modification						
Any dose with QD dosing	20 mg QW						
20 mg QW	10 mg QW						

 • Pneumonitis (Grade 1). 	
Step 1: Interrupt piasaalisib until the toxicity has resolved.
 
Step 2: Restart piasaalisib at next lower dose. Monitor as clinically indicated.
						

 • Pneumonitis (≥ Grade 2). 	Permanently discontinue piasaalisib.						

 • Skin toxicity (eg, rash, pruritus, etc, unless otherwise specified) (Grade 2-3). 	
Step 1: Interrupt piasaalisib until the toxicity has resolved to ≤ Grade 1.
 
Step 2: Restart piasaalisib at same dose. If assessed as related to piasaalisib, restart at next lower dose.
						

 • Exfoliative dermatitis (Grade 1). 	
Step 1: Interrupt piasaalisib until the toxicity has resolved.
 
Step 2: Restart piasaalisib at next lower dose. Monitor as clinically indicated.
						

 • Exfoliative dermatitis (≥ Grade 2). 	Permanently discontinue piasaalisib.						

 • Intestinal perforation (any grade). 	Permanently discontinue piasaalisib.						

 • Pneumocystis jiroveci pneumonia infection. 	Interrupt piasaalisib. Permanently discontinue piasaalisib if Pneumocystis jiroveci pneumonia infection is confirmed.						

Table 7: Guidelines for Interruption and Restarting of Study Drug (Continued)

ADVERSE EVENT	ACTION TAKEN
Other toxicities (continued)	

 • CMV infection. 	Participants with CMV viremia without associated clinical signs of CMV infection should be carefully monitored. Consider interrupting parsaclisib for participants with CMV viremia and clinical signs of infection until the infection has resolved. Restart parsaclisib reduced by 1 dose level if approved by the medical monitor.

 • Varicella zoster infection. 	Interrupt parsaclisib. Restart parsaclisib only by approval of the medical monitor.

 • Any Grade 1 or Grade 2 toxicity unless otherwise specified. 	Continue parsaclisib and treat the toxicity; monitor as clinically indicated.

 • Any Grade 3 toxicity, if clinically significant and not manageable by supportive care unless otherwise specified. 	
Step 1: Interrupt parsaclisib up to 14 days until the toxicity has resolved to \leq Grade 1.
 
Step 2: Restart parsaclisib at same dose. If assessed as related to parsaclisib, restart at next lower dose. If interrupted for > 14 days, contact the medical monitor for approval to restart parsaclisib. Monitor as clinically indicated.


 • Any recurrent Grade 3 toxicity after 2 dose reductions. 	Discontinue parsaclisib administration and follow-up per Protocol. Exceptions require approval of sponsor.

 • Any other Grade 4 toxicity. 	Discontinue parsaclisib administration and follow-up per Protocol. Exceptions require approval of sponsor.

CMV = cytomegalovirus; IV = intravenous; PCR = polymerase chain reaction.

^a Diarrhea accompanied by abdominal pain and/or mucus or blood in stool.

Table 8: Dose Levels for Parsaclisib

Timepoint	Dose
Starting dose	20 mg QD for 8 weeks (Day 1 through Day 56)
First dose reduction	10 mg QD
Second dose reduction	5 mg QD
Week 8 (Day 57) onward	2.5 mg QD ^a
First dose reduction	1 mg QD
Second dose reduction	NA

^a All participants will receive 2.5 mg QD at Week 8 (Day 57) regardless of prior dose level unless dose was modified due to diarrhea/colitis guidelines.

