5.1. Inclusion Criteria

Participants are eligible to be included in the study only if all of the following criteria apply:

1. Male or female Japanese participant who must be ≥ 18 years of age at the time of signing the ICF.
2. Ability to comprehend and willingness to sign a written ICF and comply with all study visits and procedures.

Note: For participants under 20 years old, those whose parent/legal guardian is willing/able to comply with study requirements and understand/sign the ICF. Participants themselves must sign the ICF form.

3. Histologically confirmed, relapsed or refractory, FL Grade 1, 2, and 3a.
4. Ineligible for HSCT.
5. Must have been treated with at least 2 prior systemic therapies for FL.
6. Radiographically measurable lymphadenopathy or extranodal lymphoid malignancy (defined as the presence of ≥ 1 lesion that measures > 1.5 cm in the LD and ≥ 1.0 cm in the LPD, respectively) as assessed by CT or MRI.
7. Participants must be willing to undergo an incisional, excisional, or core needle lymph node or tissue biopsy or provide a lymph node or tissue biopsy collected after the completion of last therapy. An earlier archived lymph node or tissue biopsy is acceptable if hospitalization is required for biopsy (eg, no superficial lymph node) and SUV_{max} by FDG-PET is < 14 .
8. ECOG performance status 0 to 2.
9. Life expectancy ≥ 12 weeks.

10. Adequate hematologic, hepatic, and renal function (values must not be achieved with growth factors):
 - a. ANC $\geq 1.0 \times 10^9/L$.
 - b. Hemoglobin ≥ 8.0 g/dL.
 - c. Platelet count $\geq 50 \times 10^9/L$.
 - d. Total bilirubin $\leq 1.5 \times ULN$. Participants with documented history of Gilbert's syndrome and in whom total bilirubin elevations are accompanied by elevated indirect bilirubin are eligible.
 - e. ALT/AST $\leq 2.5 \times ULN$ or $\leq 5 \times ULN$ in the presence of liver involvement.
 - f. Calculated creatinine clearance ≥ 40 mL/min by the Cockcroft-Gault Equation or the estimated glomerular filtration rate ≥ 40 mL/min/1.73 m² using the Modification of Diet in Renal Disease formula.
11. Willingness to avoid pregnancy or fathering children based on the criteria below:
 - a. Woman of nonchildbearing potential (ie, surgically sterile with a hysterectomy and/or bilateral oophorectomy OR ≥ 12 months of amenorrhea and > 50 years of age after cessation of all exogenous hormonal treatments).

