6.5.4. Criteria and Procedures for Dose Interruptions

Safety concerns should be discussed with the sponsor immediately upon occurrence or awareness to determine if the participant should continue or discontinue study treatment.

Treatment with piasclisib may be delayed up to 14 days to allow for resolution of toxicity. Participants may resume treatment if no medical condition or other circumstance exists that, in the opinion of the investigator, would make the participant unsuitable for further participation in the study. The treating investigator should contact the sponsor to discuss the case of any participant whose treatment has been delayed for more than 14 days before restarting treatment with piasclisib.

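### Table 7 has no platelet line for 25 to <50 × 10⁹/L in participants enrolled above 100, so the trigger for interrupting parsaclisib weakens as the count falls

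*Protocol*

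**What the plan says.** All counts here are in units of 10⁹/L. The hematology part of Table 7 (Protocol Section 6.5) has three platelet lines:

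- The first is for those who start with higher counts: "Platelet count is Grade 2 (50 to $< 75 \times 10^9/L$) for participants who enrolled with platelets $> 100 \times 10^9/L"
- The second is for those who start with lower counts: "Platelet count is Grade 3 ($< 50 \times 10^9/L$) for participants who enrolled with platelets $\leq 100 \times 10^9/L"
- The third is Grade 4, below 25, with no condition on the enrollment count.

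The first two share one action: hold drug for up to 14 days until recovery to Grade 1 or better or to the pretreatment level, then restart at the same dose. The Grade 4 line also calls for a hold of up to 14 days and a same-dose restart, and adds "If recurs, start at next lower dose". None of the three makes the hold depend on anything further.

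Under other toxicities, the table has a general row: "Any Grade 3 toxicity, if clinically significant and not manageable by supportive care unless otherwise specified". Its restart rule is same dose, except "If assessed as related to parsaclisib, restart at next lower dose". A hold beyond 14 days needs the medical monitor's approval to restart.

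Inclusion criterion 10c (Section 5.1) is "Platelet count $\geq 50 \times 10^9/L", so participants can enroll on either side of 100.

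**The concern.** The Grade 2 line for participants enrolled above 100 stops at 50, and the Grade 3 line is restricted to those enrolled at 100 or below. The band from 25 to <50 is therefore missing for the group that starts with the better counts. In that band the only applicable text is the general Grade 3 row, under which a site may continue dosing through a count without symptoms.

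This reverses the expected order: holding drug is required at a milder count, optional at a worse one, and required again at the worst. It also treats the group with normal or near-normal starting counts more leniently at 40 than the group that started low. A split by starting count makes sense if it avoids holding drug for pre-existing low platelets, but that reasoning points to an equal or stricter trigger above 100.

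What is at stake is participant safety and consistent handling across sites. Section 6.5.2 describes low platelets as an apparent effect of the drug class. The efficacy analysis is not involved.

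**Working it through.** The plan has no figure to reproduce here. The check is to apply each line of Table 7 to every combination of enrollment count and current count.

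**Rules, from Table 7**

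- Line A: enrolled >100 and current count 50 to <75.
- Line B: enrolled ≤100 and current count <50.
- Line C: current count <25, any enrollment count.

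**Which line applies**

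| Current count | Enrolled >100 | Enrolled ≤100 |
|---|---|---|
| 50 to <75 | A: hold | none; general Grade 1–2 row: continue |
| 25 to <50 | **none; general Grade 3 row: conditional hold** | B: hold |
| <25 | C: hold | B and C: hold |

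Stepping through whole-number counts from 0 to 74 with an enrollment count of 150, those matching no line run from 25 to 49 without a break. With an enrollment count of 90, every count below 50 matches a line.

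Two cells match no hematology line. In the group enrolled at ≤100, the unmatched cell is the mildest one, so the order is still continue, hold, hold. In the group enrolled at >100, the order is hold, conditional hold, hold. Only that one is out of sequence.

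**Worked examples (illustrative enrollment counts)**

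- Enrolled at 180: at 60, hold and restart at the same dose; at 40, hold only if the general row's conditions are met; at 20, hold and restart at the same dose, stepping down if it recurs.
- Enrolled at 90: at 40, hold.
- Fall to 40 from 180: 1 − 40/180 = 77.8%. Fall to 40 from 90: 1 − 40/90 = 55.6%. The larger fall has the weaker trigger. Table 7 works on absolute counts, so these percentages only illustrate the contrast.

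**When the gap is reached**

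A participant seen at 50 to <75 is already off drug under line A. The gap matters only when the first low value recorded lies in 25 to <50. Protocol Table 4 schedules hematology at Weeks 2 and 6 and every 4 weeks from Week 4 to Week 48, which is 2 + 12 = 14 draws after Day 1. The intervals are four of 2 weeks (to Week 8) and ten of 4 weeks ((48 − 8)/4 = 10). After Week 48 the interval is 12 weeks. A count could pass through 50 to <75 unseen between draws.

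**Other text that might close the gap**

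Section 6.5.2 gives advice on reporting bleeding and infection but no count. Section 6.5.4 sets the 14-day limit and asks for discussion with the sponsor but no count. If the exception in the general Grade 3 row for matters specified elsewhere is read as excluding platelets, the band has no row at all. On either reading there is no unconditional hold.

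**The case against.** The band is not without guidance: the general Grade 3 row covers it, and its restart rule is stricter than the hematology rows, since a related event restarts at a lower dose. Table 7 is also guidance. Section 6.5 says "Individual decisions regarding dose interruption and reduction should be made using clinical judgment and in consultation with the" medical monitor, and Section 6.5.4 says "Safety concerns should be discussed with the sponsor immediately upon occurrence or awareness". An investigator told to hold at 60 is unlikely to see no need at 40. The path to harm is narrow, because anyone first seen at 50 to <75 is already off drug. Thrombocytopenia is on neither the protocol's nor the SAP's list of adverse events of special interest, nor among the SAP's laboratory events of special interest. Finally, the proposed wording would remove the lower-dose restart for a related Grade 3 event.

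Most of this stands, and it limits the weight of the point. It does not answer it. The claim concerns the trigger only, and there the table's own order is inverted. Judgment and consultation may lead a site to the sensible action, but nothing in those provisions restores the hold, and two sites could handle the same count differently. As for the restart, a same-dose restart is what the table already prescribes for Grade 3 in the group enrolled at ≤100 and for a first Grade 4 event, so the loss is small.

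**Conclusion.** The concern holds. For participants enrolled above 100, Table 7 requires a hold at 50 to <75 and below 25 but only conditionally at 25 to <50. It is the one place in the platelet rules where the trigger relaxes as the count worsens.

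The size is modest. The number of participants affected is unknown, since the documents give neither a thrombocytopenia rate nor the distribution of enrollment counts. Exposure to the gap requires a first low reading inside the band and a decision that the general row's conditions are not met. The conclusion rests on the table as printed and assumes nothing about how often sites follow it literally. It does not bear on the response-rate estimate, its confidence interval or the sample size. It should be corrected as a minor safety clarification.

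**What to change.** In Table 7, for participants enrolled above 100, change the Grade 2 entry (50 to <75) to Grade 2 or 3 (25 to <75). Keep the existing action: hold up to 14 days until Grade 1 or better or the pretreatment level, then restart at the same dose. Leave Grade 4 (<25) in its own row. Every count below 75 in this group then matches a hematology line with an unconditional hold.

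The trade-off is that a related Grade 3 event in this group would no longer restart at the next lower dose. If the sponsor wants to keep a reduction, add a step-down on recurrence to the line, as the Grade 4 row already has.

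The cost is one line of text, with no new tests, visits or analyses. Section 11.1 requires sponsor and then IRB/IEC approval for changes to protocol procedures, so a letter to investigators would not be enough on its own. The change can go into the next amendment, with a clarification to sites in the meantime. It remains useful despite the earlier study closure, because Section 6.7 lets participants continue on drug after the end of the study.

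### Protocol Table 7: for participants enrolled with platelets above 100 × 10^9/L, a count of 50 to < 75 after a Grade 4 event is both a restart level and an interruption trigger

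*Protocol*

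**What the plan says.** All counts below are in units of 10^9/L.

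The hematology part of Table 7 (Protocol Section 6.5) has two rows.

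- **First row.** The triggers are ANC below 1.0 (Grade 3) and two platelet conditions that depend on the count at enrolment. The one that matters here is "Platelet count is Grade 2 (50 to $< 75 \times 10^9/L$) for participants who enrolled with platelets $> 100 \times 10^9/L". For those enrolled at 100 or below, the platelet trigger is a count under 50 (Grade 3). The drug is interrupted for up to 14 days, until the toxicity is no worse than "Grade 1 or pretherapy baseline. For Grade 3 ANC, monitor at least weekly", and is then restarted at the same dose.
- **Grade 4 row.** The triggers are ANC below 0.5, Grade 3 or 4 febrile neutropenia, and platelets below 25. The drug is interrupted for up to 14 days, until the toxicity is no worse than "Grade 2. (Monitor ANC at least weekly". It is then restarted at the same dose, with a step down only if the event recurs.

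Section 6.5 leaves individual decisions to clinical judgment together with the medical monitor. Section 6.5.4 asks for contact with the sponsor when a delay exceeds 14 days. Section 7.1.1 makes discontinuation mandatory for a persistent adverse event that needs a delay of more than 14 days, unless the sponsor has approved a longer one.

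**The concern.** The Grade 4 row lets a participant restart in a platelet range that the first row names as a reason to stop. Take someone enrolled at 150 who falls below 25 and recovers to 60. One row says restart at the same dose; the other says interrupt until Grade 1 or baseline.

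The 14-day limit gives this practical weight. If the count is still 60 on day 14, the Grade 4 row permits restart. The first row keeps the drug on hold, and the participant then reaches the discontinuation criterion of Section 7.1.1 unless the sponsor approves a longer delay. The same laboratory course can therefore end in continued treatment or in discontinuation.

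The choice also reaches the analysis. SAP Section 6.4 summarises dose interruptions, and SAP Section 9.2.3 tabulates adverse events that lead to interruption or discontinuation. Protocol Section 6.5.2 describes thrombocytopenia as an apparent class effect, so these rows cover a toxicity that the sponsor expects.

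**Working it through.** No sample size, power or error-rate figure bears on this point, so there is no stated figure to reproduce. The check is to find the values that satisfy both the restart condition of the Grade 4 row and the trigger of the first row.

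**Inputs, all from Table 7 unless noted**

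- Platelet grades: Grade 2 is 50 to < 75, Grade 3 is < 50, Grade 4 is < 25. So no worse than Grade 2 means ≥ 50, and no worse than Grade 1 means ≥ 75.
- ANC grades: Grade 3 is < 1.0, Grade 4 is < 0.5. I infer from the Grade 3 bound that no worse than Grade 2 means ≥ 1.0.
- Entry floors (Section 5.1, criterion 10): platelets ≥ 50 and ANC ≥ 1.0. Participants can therefore enrol on either side of the 100 cut.

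**Comparison**

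| Group | First row interrupts at | Grade 4 row permits restart at | Values meeting both |
|---|---|---|---|
| Platelets, enrolled > 100 | 50 to < 75 | ≥ 50 | 50 to < 75 |
| Platelets, enrolled ≤ 100 | < 50 | ≥ 50 | none |
| ANC | < 1.0 | ≥ 1.0 | none |

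Listing whole-number platelet counts for enrolment values of 60, 90, 100, 101 and 150 gives the same answer. The overlap is 50 to 74 at 101 and 150, and there is none at 60, 90 or 100.

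**Does the baseline alternative remove the overlap?** No. In the affected group the baseline is above 100, so a count of 50 to < 75 reaches neither Grade 1 (≥ 75) nor baseline.

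**Does the table rank the rows?** No. The first row is not limited to events that begin at Grade 2, and no precedence is stated. If the participant restarts at 60 and the next hematology draw is again 60, the first row's trigger is met.

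**The case against.** The best defence is that Table 7 is headed as guidelines and is organised by event. On that reading the Grade 4 row governs an episode that reached Grade 4 until the drug is restarted, and the first row governs an episode that presents at Grade 2. Clinical judgment, the medical monitor and the sponsor contact in Section 6.5.4 then limit variation between sites. This is a reasonable reading, and it makes the conflict less severe than two rules that no site could apply. But the table does not state it, and it does not say what to do when the first count after restart is still 50 to < 75. The allowance in Section 6.5 for transient laboratory values (≤ 72 hours) concerns dose reduction and does not choose between the rows.

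Four stronger readings are tempting, and the documents do not support them.

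- **That ANC has the same contradiction.** It does not: restart is at ≥ 1.0 and the trigger is < 1.0. The recovery levels only differ, at Grade 2 or better after Grade 4, and Grade 1 or baseline after Grade 3. For a participant whose baseline ANC was already at Grade 2 level, the baseline alternative removes even that difference. A looser condition after the more severe event may look odd, but it can be followed and may be deliberate.
- **That every participant is exposed.** The overlap needs enrolment above 100.
- **That about 8 of 40 are affected.** Section 2.1.3 reports 19% Grade 3/4 neutropenia in Study INCB 50465-101, and 0.19 × 40 = 7.6. That rate concerns neutropenia, where there is no overlap, so it does not size the platelet conflict.
- **That each pause alters treatment duration.** SAP Section 6.4 takes last dose minus first dose plus 1 and does not subtract interrupted days. A longer pause alone leaves it unchanged.

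**Conclusion.** The contradiction is real and narrow. It covers participants "for participants who enrolled with platelets" above 100 who have a Grade 4 platelet count and recover into 50 to < 75. For them the whole Grade 2 band is both a restart level and an interruption trigger, the baseline alternative gives no way out, and no text says which row governs.

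This conclusion rests on the grade bounds printed in Table 7 and on reading the first row as applying to any count in its range. If the sponsor intended the event-based reading, the defect is a missing statement of precedence, and it still needs correcting.

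The number affected is unknown and may be small, because the documents give no Grade 4 platelet rate. What can change is whether an individual restarts or moves towards the 14-day criterion, together with the descriptive counts of interruptions and discontinuations. No effect on the primary endpoint is shown. I take no view on which recovery level is right.

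**What to change.** Reconcile the two hematology rows of Table 7 so that no platelet count is at once a restart level and an interruption trigger. Alternatively, state in the table which row governs a participant recovering from Grade 4 platelets, including when the count is still 50 to < 75 after restart. The sponsor's clinical team must decide which condition applies.

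The ANC entries do not need to change to remove the contradiction. The cost is wording in one table of the protocol, with no added procedures and no change to the SAP's methods.
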